6.2 Treatment Regimens

There are 2 treatment groups in this study. Subjects will be randomized to either SC placebo or SC Abatacept (as randomized group) at the beginning of the study and each subject is expected to receive their randomized treatment (SC placebo or SC abatacept) throughout the double-blind period.

During the open-label period and beyond until study completion as per protocol/withdrawal all subjects will receive weekly SC abatacept injections.

6.3 Populations for Analyses

Efficacy endpoints will be summarized according to the Intent-to-Treat (ITT) population and safety endpoints will be summarized according to the as-treated analysis population. These populations are described briefly below along with other populations.

- **Intent-to-Treat Analysis Population:**

The Intent-to-Treat (ITT) analysis Population is defined to include all subjects randomized into the study for whom Case Report Form (CRF) data indicate that at least one dose of study medication (abatacept or placebo) is administered during the double-blind period.

All subjects who are randomized but never received study medication are to be excluded. Given the blinded nature of this study, it is reasonable to assume that subjects who discontinue prior to the receipt of study medication do so for reasons unrelated to study medication. Subjects are grouped according to the treatments to which they are randomized by IXRS.

ITT analysis population is also referred to as “All Randomized and Treated Subjects”.

- **As-Treated Analysis Population:**

The As-Treated analysis population contains all subjects for whom CRF data indicate that at least one dose of study medication was administered during double-blind period.

Subjects are grouped according to the treatments to which they are randomized, except in cases where information is available, which indicates that a subject receives a different treatment for the entire course of double-blind period. In this case, the subject will be presented by the treatment they actually received.

The As-Treated analysis population will also be referred as “All Treated Subjects”.

- **Per-Protocol Analysis Population:**

The Per-Protocol analysis population is defined as a subset of the ITT analysis population which excludes subjects who have relevant protocol deviations during the double-blind study period. Relevant protocol deviations are those protocol deviations that might affect the primary efficacy endpoint of the study. A programmable list of relevant protocol deviation criteria is included in [APPENDIX 1](#).

The analysis of the primary efficacy endpoint will be repeated in the Per-Protocol analysis population. The Per-Protocol analysis population will exclude subjects with at least 1 relevant protocol deviation.

- **Open-Label Treated Analysis Population:**

The Open-Label treated analysis population will contain all subjects for whom CRF data indicate that at least one dose of study medication was administered during the open-label period. All Week 52 analyses will be performed using this population except otherwise specified.

- **Japan Open-Label Extension Treated Analysis Population:**

The Japan Open-Label Extension treated analysis population will contain all subjects from Japan for whom CRF data indicate that at least one dose of study medication was administered during the open-label extension period. All Week 76 analyses will be performed using this population except otherwise specified.

- **Long-Term Extension Treated Analysis Population:**

The Long-Term Extension treated analysis population will contain all subjects (except for U.S. or Czech subjects) for whom CRF data indicate that at least one dose of study medication was administered during the long-term extension period. All Year 3 (3.5 year in Japan subjects) analyses will be performed using this population except otherwise specified.

█ [REDACTED]

7 STATISTICAL ANALYSES

The analyses for this study is scheduled to be performed at 4 separate time points:

- 17) End of Double-Blind period (Week 24) for all subjects.
- 18) End of Open-Label period (Week 52) for all subjects.
- 19) End of Open-Label Extension period (Week 76) for sites in Japan.
- 20) And end of the study (completion of Long-Term Extension period and Follow-up period).

The double-blind period (Week 24) analysis will be performed once all subjects complete their Week 24 visit assessment or discontinue prematurely prior to Week 24. This analysis will include the analyses of the primary efficacy endpoint, secondary and exploratory efficacy endpoints up to Week 24 and safety analyses for the 24-week double-blind period. Safety analyses will include all the adverse events (AEs) reported in the study up to first dose date in the open-label period, or 56 days after the last dose date in the double-blind period whichever is earlier. Nominal p-values will be provided for the secondary endpoint measures at Day 169 (Week 24), no formal statistical testing will be conducted for any of the efficacy analyses related to the secondary endpoints at other time points and on any of exploratory endpoints. Appropriate summary statistics will be provided for the analysis of each endpoint.

The open-label period (Week 52) analysis will be performed once all subjects complete 52 weeks of treatment in the study. This analysis will include summaries of AEs reported during the open-label period. Efficacy endpoints will be summarized over time during the open-label period. No formal statistical testing will be conducted for any of the efficacy analyses. Appropriate summary statistics will be provided for the analysis of each endpoint. The 52-week analysis will be performed using the open-label treated analysis population. Selected outputs for the OL period will be detailed in the DPP.

The open-label extension period (Week 76) analysis will be performed, using only Japanese sites, once all subjects at Japanese sites complete 76 weeks of treatment in the study. This analysis will include summaries of AEs reported during the open-label extension period. Efficacy endpoints

will be summarized over time during the open-label extension period. No formal statistical testing will be conducted for any of the efficacy analyses. The open-label extension period analysis will be performed using the Japan open-label extension treated analysis population. Selected outputs for the OLE period will be detailed in the DPP.

The final analysis will be performed once all subjects complete the (3 year) long-term extension period and/or follow-up visits whichever is later. This analysis will include summaries of AEs reported during the long-term extension period (for open-label extension treated subjects) and the cumulative abatacept period (for abatacept treated subjects in the study) up to 56 days post last dose date in the study. The long-term extension period analysis will be performed using the long-term extension treated analysis population.

7.1 General Methods

The table below provides an overview of the efficacy analyses to be performed. These are thought to be robust in the case of the small marginal strata (Japan) frequencies of 20 or more (10 per treatment group); otherwise, some strata may be dropped from the models.

Table 7.1-1: Planned Efficacy Analyses

Measure of Interest	Analysis Method
IMACS DOI at Day 169 (Week 24)	
Primary Analysis:
 Using a logistic regression model that includes treatment group, stratification factors: disease diagnosis (DM vs. Non-DM), ILD (absent vs. present), Region (Japan vs. ROW), baseline MMT8 score, baseline MDAAT, and baseline PGA. Point estimate of adjusted ORs, corresponding 95% CI and p-value will be provided. The proportion of subjects in IMACS DOI in each treatment group and corresponding 95% CI will also be provided.
Time to event (IMACS DOI at 2 consecutive time points) up to Day 169 (Weeks 12 and 24)	Point estimates and 95% CIs for the hazard ratio of abatacept versus placebo will be based on Cox proportional hazards models. The stratification factors: disease diagnosis (DM vs. Non-DM), ILD (absent vs. present), Region (Japan vs. ROW), baseline MMT8 score, baseline MDAAT and baseline PGA will be included in the model. Observations from subjects who discontinue due to lost to follow-up will be censored at the date of last available data in the study. The date of the first IMACS DOI of the 2 consecutive IMACS DOI events will be used in the analysis. Estimate the distribution of time to first occurrence of event using Kaplan-Meier method/curve.
Changes from baseline in continuous variables (i.e., FI-2 scores, MRC total improvement score, IMACS core components, XXXXXXXXXX)	Longitudinal (repeated measures) model [including treatment group, baseline value of variable and randomization stratification factors: disease diagnosis (DM vs. Non-DM), ILD (absent vs. present), Region (Japan vs. ROW), time (categorical as study visit at which variable was measured), time by baseline value of variable and time by treatment as fixed effects and subject as a random effect], adjusted mean, SE, 95% CI for adjusted mean difference between treatment groups will be provided for all time

Table 7.1-1: Planned Efficacy Analyses

Measure of Interest	Analysis Method
	points. In addition, nominal p-values will be provided for the secondary endpoints of change from baseline at Day 169 (week 24) analysis.
Differences in proportions (i.e., proportion of subjects achieving IMACS DOI at Day 169 (Week 24), etc.)	Point estimate of response rate, 95% CI, point estimates and 95% CI of treatment difference adjusted for randomization stratification factors: disease diagnosis (DM vs. Non-DM), ILD (absent vs. present), Region (Japan vs. ROW) (based on minimum risk weights).
Differences in proportions (i.e., proportion of subjects achieving IMACS DOI in myositis Ab negative or positive subjects, etc.)	Point estimate of response rate, 95% CI, point estimates and 95% CI of treatment difference adjusted for randomization stratification factors: disease diagnosis (DM vs. Non-DM), ILD (absent vs. present), Region (Japan vs. ROW) (based on minimum risk weights).

All construction of CIs for differences in response rates between treatment groups will be based on minimum risk weights⁷ to account for randomization stratification factors, unless otherwise noted. All construction of CIs for response rates within treatment group will be based on normal approximation methods, unless otherwise noted.

All construction of CIs for continuous measures will be based on a longitudinal repeated mixed effects model which includes treatment group, baseline value of variable, randomization stratification factors (diagnosis [DM vs. Non-DM], ILD [absent vs. present], Region [Japan vs. ROW]), time (as categorical variable), and time by treatment interaction as fixed effects and subject as a random effect. An unstructured covariance matrix will be used to model the correlation of the repeated measures within each subject. The SAS procedure PROC MIXED will be used with the restricted maximum likelihood (REML) method for estimation and the denominator degrees of freedom calculated according to the Kenward Roger method. The parameter estimations will be based on assumption of data being missing at random (MAR) using the method of restrictive maximum likelihood (REML). MAR means that given the observed data (e.g. for patients who discontinue up to the day they discontinue), the missingness mechanism does not depend on the unobserved data. In other words, this analysis assumes that a patient who drops out has the same conditional distribution (of the unobserved data after dropout given the observed data) as patients who share the same observed data and do not drop out. In case of non-convergence of the preferred longitudinal model or memory space issues the following back-up model will be used: a compound symmetry (CS) covariance matrix will be used to model the correlation of the repeated measures with each subject.

Unless otherwise specified, summary statistics will include the following:

- Summary statistics for continuous variables will include means, standard deviations, minima and maxima.

Summary statistics for qualitative or discrete variables will include the count and percentage.

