Nominal p-values will be provided for the secondary efficacy endpoints at Day 169 ie, mean change from baseline at Day 169 for each of the secondary endpoints: FI-2, HAQ-DI, MDAAT and MRC. The mixed longitudinal model will account for any missing values on any of the secondary efficacy endpoints. All construction of CIs for differences in response rates between treatment groups will be based on minimum risk weights to account for randomization stratification factors, unless otherwise noted. All construction of CIs for response rates within treatment group will be based on normal approximation, unless otherwise noted.

Efficacy assessments collected at week 24 on subjects who discontinue study medication prior to week 24 will not be included in the primary analyses of the secondary endpoints, but will be included in a sensitivity analysis of the secondary endpoints. The mixed longitudinal model will be considered the primary analyses for all the continuous secondary endpoints, specifications of

sensitivity analyses of the secondary endpoints under different assumptions for missing data, including the use of efficacy data collected after discontinuation from the study, will be provided in the SAP.

A summary of the analysis methods to be used for the analysis of the primary, secondary and exploratory efficacy endpoints are presented in Table 8.4.2.2-1 below. Further details on the primary and secondary analyses along with exploratory evaluations, any sensitivity analyses and data handling details regarding issues such as missing data will be provided in the Statistical Analysis Plan. Analyses specific to the MRI sub-study, Muscle Biopsy sub-study, and Actigraphy will be presented in the Statistical Analysis Plan.

Table 8.4.2.2-1: Planned Efficacy Analyses	
Measure of Interest	Analysis Method
IMACS DOI at Day 169 (Week 24)	Primary Analysis: Using a logistic regression model that includes treatment group, stratification factors: disease diagnosis (DM vs non-DM IIM), ILD (absent vs present), Region (Japan vs ROW), and baseline MMT8, baseline MDAAT, and baseline PGA as continuous variable. Point estimate of adjusted ORs, corresponding 95% CI and p-value will be provided. The proportion of subjects in IMACS DOI in each treatment group and corresponding 95% CI will also be provided.

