1 BACKGROUND [REDACTED]

[REDACTED]

[REDACTED]

[REDACTED]

[REDACTED]

IIM who had persisting signs of active disease after treatment with glucocorticoids and one

[REDACTED]

Research Hypothesis:

Subcutaneous abatacept (125mg weekly) in combination with standard treatment will achieve a higher rate of responders, defined as the percentage of subjects who achieve the IMACS DOI (International Myositis Assessment and Clinical Studies - definition of improvement), after 24 weeks of treatment versus standard treatment alone in adult subjects with active IIM.

Schedule of Analyses:

The analyses for this study is scheduled to be performed at 4 separate time points:

- 1) End of Double-Blind period (Week 24) for all subjects.
- 2) End of Open-Label period (Week 52) for all subjects.
- 3) End of Open-Label Extension period (Week 76) for sites in Japan. The purpose is to obtain 52 week abatacept efficacy data on all Japanese subjects for submission, specifically here the Japanese subjects originally randomized to placebo.
- 4) End of the study (completion of Long-Term Extension period and Follow-up period).

The Double-Blind period (Week 24) analysis will be performed once all subjects complete their Week 24 visit assessment or discontinue prematurely prior to Week 24. The Week 24 analysis will include the analyses of the primary efficacy endpoint, secondary and exploratory efficacy endpoints up to Week 24 and safety analyses. A subgroup analysis (selected outputs identified in DPP) on Japan subjects alone will be conducted for Japanese submission purposes. Actigraphy data and data from the Muscle Biopsy sub-study will be not be part of the initial Double-Blind period (Week 24) database lock and will be reported separately.

The Open-Label period (Week 52) analysis will be performed once all subjects complete 52 weeks of treatment in the study. A subgroup analysis (selected outputs identified in DPP) on Japan subjects alone will be conducted for Japanese submission purposes.

The Open-Label Extension period (Week 76) analysis will be performed, using only Japanese sites, once all Japanese subjects complete their Week 76 visit assessment. Selected outputs only identified in DPP.

The final analysis will be performed when all subjects have completed the 3 year long-term extension, (3.5 years for Japan subjects by including OLE data) and/or follow-up visits whichever is later.

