11.6.1 Other Efficacy Analyses

IMACS DOI

Proportion of subjects in IMACS DOI over time during the study will be presented by the double-blind treatment groups and visit. Point estimate of response rate, 95% CI, point estimates and 95% CI of treatment difference adjusted for randomization stratification factors: disease diagnosis (DM vs. Non-DM), ILD (absent vs present), Region (Japan vs ROW) (based on minimum risk weights).

Proportion of subjects who meet the $\geq 20\%$ improvement from baseline over time for each of the core measures of IMACS (PGA, SGA, MMT-8, HAQ-DI, MDAAT and muscle enzymes) will be presented by double-blind treatment groups and visit. Point estimate of response rate, 95% CI, point estimates and 95% CI of treatment difference adjusted for randomization stratification factors: disease diagnosis (DM vs. Non-DM), ILD (absent vs present), Region (Japan vs ROW) (based on minimum risk weights).

The proportion of subjects in IMACS Minimal, Moderate and Major responses using the Myositis Response Criteria tool (as defined in [section 8.1.11](#)) will also be presented over time during the study. Point estimates and 95% CI within each treatment group for IMACS Minimal, Moderate and Major DOI response will be provided by visit. Differences in IMACS Minimal, Moderate and Major DOI response rates between the double-blind treatment groups will be provided by point estimate and corresponding 95% CIs based on an ordinal logistic regression model.

Additional separate longitudinal repeated mixed effects models will be used to assess the mean change from baseline over time in the study in each of the IMACS core measures (PGA, SGA, MMT-8, HAQ-DI, MDAAT and muscle enzymes). The mixed models will include double-blind treatment group, baseline measurement, randomization stratification factors: disease diagnosis (DM vs. Non-DM), ILD (absent vs present), Region (Japan vs ROW), time (study days in which each core measure was collected), time by baseline measurement and time by treatment interactions as fixed effects and subject as a random effect. Adjusted mean, SE, 95% CI for adjusted mean difference between treatment groups will also be provided. The estimate of baseline mean core measure, mean post-baseline core measure, and adjusted mean change from baseline core measure will be also be presented by double-blind treatment group and visit.

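### Within-group response-rate intervals default to the normal approximation with no readable exception for small groups; naming the Wilson score method would put this descriptive output right

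*SAP*

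**What the plan says.** SAP 7.1 states the rule for one-group percentages: "All construction of CIs for response rates within treatment group will be based on normal approximation methods, unless otherwise noted". Protocol 8.4.2.2 agrees: "All construction of CIs for response rates within treatment group will be based on normal approximation, unless otherwise noted". Neither says which normal-approximation interval is meant (plain Wald, continuity-corrected or score). The readable text names no other method for within-group rates, and Appendix 3 of the SAP, which covers the open-label and extension analyses, gives none of its own.

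The rule reaches small groups in several places:

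- **Japan only, Weeks 24 and 52.** SAP 1 states: "A subgroup analysis (selected outputs identified in DPP) on Japan subjects alone will be conducted for Japanese submission purposes".
- **Japan only, Week 76.** SAP 7 states: "The open-label extension period analysis will be performed using the Japan open-label extension treated analysis population".
- **Rates by visit.** SAP 11.6.1 plans within-group rates and 95% intervals for IMACS DOI and for each core measure. For the graded response it says: "Point estimates and 95% CI within each treatment group for IMACS Minimal, Moderate and Major DOI response will be provided by visit". SAP 11.6 makes these analyses as observed, without imputation or p-values.
- **Autoantibody subgroups.** Table 7.1-1 lists response rates with 95% intervals in antibody-negative and antibody-positive subjects.

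The only remark on small numbers comes just before Table 7.1-1: "These are thought to be robust in the case of the small marginal strata (Japan) frequencies of 20 or more (10 per treatment group". Below that size the stated fallback is to drop strata from the models, which does nothing for a one-group percentage.

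**The concern.** The usual normal-approximation interval for a proportion is unreliable in small samples. It is centred on the observed rate, its width comes from the observed rate alone, and it shrinks to nothing when nobody or everybody responds. The Japan tables are meant for a regulatory submission, and the open-label tables carry no p-values, so the interval printed beside each percentage is the main statement of its uncertainty. A limit below 0% or above 100%, or an interval of zero width at 10 out of 10, would mislead a reader or need explaining. A nominal 95% interval that covers less often than that misstates what is known about the group.

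**Working it through.** **Inputs.** Confidence level 95% (SAP Table 7.1-1). Planning rates 60% and 33%, with 75 per arm (SAP 5). Ten per group is the SAP 7.1 robustness threshold; 20 per group is an assumed larger case. Neither document gives a planned Japan enrolment or any coverage figure, so there is no stated value to reproduce.

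**Formulas.** For x responders out of n, with p̂ = x/n and z = 1.96:

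- Wald: p̂ ± z·√(p̂(1−p̂)/n)
- Wilson: [p̂ + z²/(2n) ± z·√(p̂(1−p̂)/n + z²/(4n²))] / (1 + z²/n)
- Exact coverage at a true rate p: the sum of the binomial probabilities P(X = x) over every x whose interval contains p.

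**Step 1. Intervals at n = 10**

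| x | Wald (%) | Width | Wilson (%) | Width |
|---|---|---|---|---|
| 0 | 0 to 0 | 0 | 0 to 27.8 | 0.28 |
| 1 | −8.6 to 28.6 | 0.37 | 1.8 to 40.4 | 0.39 |
| 2 | −4.8 to 44.8 | 0.50 | 5.7 to 51.0 | 0.45 |
| 3 | 1.6 to 58.4 | 0.57 | 10.8 to 60.3 | 0.50 |
| 5 | 19.0 to 81.0 | 0.62 | 23.7 to 76.3 | 0.53 |

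Counts above 5 mirror these, so the Wald upper limit is 104.8% at 8/10 and 108.6% at 9/10, and at 10/10 the interval is 100% to 100%.

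**Step 2. Coverage at n = 10**

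- True rate 33%: Wald contains 33% for x = 2 to 6. Sum: 0.199 + 0.261 + 0.225 + 0.133 + 0.055 = 0.873. Wilson also contains it at x = 1 (0.090), giving 0.963.
- True rate 60%: Wald contains 60% for x = 4 to 8. Sum: 0.1115 + 0.2007 + 0.2508 + 0.2150 + 0.1209 = 0.899. Wilson adds x = 3 (0.0425) and x = 9 (0.0403), giving 0.982.
- True rate 10% (90% by symmetry): Wald contains 10% for x = 1 to 4. Sum: 0.3874 + 0.1937 + 0.0574 + 0.0112 = 0.650. The zero count, probability 0.9¹⁰ = 0.349, always misses. Wilson contains it for x = 0 to 2: 0.3487 + 0.3874 + 0.1937 = 0.930.

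**Step 3. Where the misses come from.** At a true rate of 60%, the Wald interval for 3/10 is the wider of the two (0.57 against 0.50) but stops at 58.4% and misses; Wilson reaches 60.3%. At 33%, the two intervals for 1/10 are almost equally wide, and only Wilson reaches 33%. Wald is wider than Wilson for every count from 2 to 8. Those counts have probability 89% at a true rate of 33% and 95% at 60%.

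**Step 4. Coverage by group size**

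| n per group | Method | 33% | 60% | 10% or 90% | Mean, 20–80% |
|---|---|---|---|---|---|
| 10 | Wald | 87.3% | 89.9% | 65.0% | 89.6% |
| 10 | Wilson | 96.3% | 98.2% | 93.0% | 95.4% |
| 20 | Wald | 90.1% | 92.8% | 87.6% | 92.2% |
| 20 | Wilson | 94.6% | 96.3% | 95.7% | 95.2% |
| 75 | Wald | 94.8% | 94.0% | 94.3% | 94.2% |
| 75 | Wilson | 95.1% | 95.6% | 95.0% | 95.0% |

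Means are over a grid of true rates in steps of 0.001.

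**Step 5. Continuity-corrected Wald** (limits moved out by 1/(2n)). At n = 10 coverage is 96.3% at 33% and 94.1% at 60%, but still 65.0% at 10% or 90%. At 0/10 its upper limit is only 5%.

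**Step 6. Chance of a zero-width Wald interval at n = 10**, p¹⁰ + (1−p)¹⁰: 1.8% at 33%, 0.6% at 60%, 34.9% at 10% or 90%.

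**The case against.** Several points on the other side stand.

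- **Ten per group is not a planned size.** A reader might infer that the SAP expects 10 Japanese subjects per arm. The sentence only gives a size above which the analyses are thought robust; Japan groups could be larger or smaller.
- **The 65% figure needs a true rate near 10% or 90%.** The documents state no such rate. At their own planning rates the shortfall at n = 10 is about 5 to 8 points, and zero-width intervals are rare. Low rates are still possible on some planned rows: SAP 11.6.1 reports the share with at least 20% improvement in MMT-8, the scale stops at 150, and entry allows scores up to 135. A subject starting at 126 can gain at most 24/126 = 19.0%. How many subjects start above 125 is not given.
- **Plain Wald is not named**, and both documents leave room for exceptions. Parts of the SAP are redacted and the Japan outputs are deferred to the DPP, so an exception may exist out of sight. Leaving the interval type open is itself a gap, and continuity correction does not cure the extremes.
- **The intervals are not uniformly too narrow.** A reader might infer from the coverage that all small-group error bars overstate precision. Step 3 shows otherwise.
- **No planned inference rests on these intervals.** The primary test is the adjusted odds ratio (SAP 7.5.2). Differences between arms use minimum risk weights or, for the graded response, ordinal logistic regression.

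These points limit the size of the concern. They do not supply a small-sample rule.

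**Conclusion.** The concern holds as a minor correction to descriptive output. The default, read as the usual Wald interval, performs poorly in groups of the size at which the SAP calls its analyses robust: coverage of about 87% to 90% at the planning rates, about 90% on average over 20% to 80%, 65% at 10% or 90%, zero width at 0/10 and 10/10, and impossible limits at 1, 2, 8 and 9 out of 10. Doubling the group to 20 raises the average to about 92%.

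This rests on three assumptions: that plain Wald is meant, that the SAP 7.1 default carries into Appendix 3 and the Japan tables, and that redacted text and the DPP hold no exception. A reader might go further and doubt the main results. The documents do not support that: at 75 per arm Wald covers 94.8% at 33% and 94.0% at 60%, and the primary comparison does not use these intervals.

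**What to change.** In SAP 7.1 and Protocol 8.4.2.2, replace the reference to the normal approximation for within-group response rates with the Wilson score method. Suggested wording: *95% confidence intervals for response rates within a treatment group will be calculated by the Wilson score method.* Add a cross-reference in SAP Appendix 3 so that the open-label, Japan extension and long-term tables follow the same rule, and use it for the Japan outputs listed in the DPP.

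The cost is one phrase in each document and one programming option. Intervals become asymmetric, somewhat narrower at mid-range counts (0.53 instead of 0.62 at 5/10) and wider at or near 0% and 100% (0.28 instead of 0 at 10/10). No test, endpoint or sample size changes, and the full-arm intervals hardly move.
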